 - Hematologic intolerance: Patients with grade 3 or 4 toxicity (absolute neutrophil count [ANC] or platelets) while on therapy that is recurrent after dose reduction to the lowest doses recommended by manufacturer
6. Eastern Cooperative Oncology Group (ECOG) performance status (PS) of 0, 1, or 2
7. Adequate end organ function as defined by (as per central laboratory tests):
 - Total bilirubin $\leq 1.5 \times$ ULN except for patients with Gilbert's syndrome who may only be included if total bilirubin $\leq 3.0 \times$ ULN or direct bilirubin $\leq 1.5 \times$ ULN

- Aspartate transaminase (AST) $\leq 3.0 \times \text{ULN}$
 - Alanine transaminase (ALT) $\leq 3.0 \times \text{ULN}$
 - Serum lipase $\leq 1.5 \times \text{ULN}$. For serum lipase $> \text{ULN} - \leq 1.5 \times \text{ULN}$, value must be considered not clinically significant and not associated with risk factors for acute pancreatitis
 - Alkaline phosphatase $\leq 2.5 \times \text{ULN}$
 - Creatinine clearance $\geq 50 \text{ mL/min}$ as calculated using Cockcroft-Gault formula
8. Patients must avoid consumption of grapefruit, Seville oranges or products containing the juice of each during the entire study and preferably 7 days before the first dose of study medications, due to potential CYP3A4 interaction with the study medications. Orange juice is allowed.
9. Written informed consent obtained prior to any screening procedures.
- 10a. Patients must have the following electrolyte values (as per central laboratory tests) within normal limits or corrected to be within normal limits with supplements prior to first dose of study medication:
- Potassium (potassium increase of up to 6.0 mmol/L is acceptable at study entry if associated with creatinine clearance within normal limits)
 - Total calcium (corrected for serum albumin); (calcium increase of up to 12.5 mg/dl or 3.1 mmol/L is acceptable at study entry if associated with creatinine clearance within normal limits)
 - Magnesium, with the exception of magnesium increase $> \text{ULN} - 3.0 \text{ mg/dL}$; $> \text{ULN} - 1.23 \text{ mmol/L}$ associated with creatinine clearance (calculated using Cockcroft-Gault formula) within normal limits.
11. Evidence of typical BCR-ABL1 transcript [e14a2 and/or e13a2] at the time of screening which are amenable to standardized RQ-PCR quantification.

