6.3 Dose modifications

6.3.1 Dose modification and dose delay

[figure not shown]
For patients who do not tolerate the protocol-specified dosing schedule, dose interruptions and/or reductions are either recommended or mandated in order to allow the patient to continue the study treatment.

These dose modifications are summarized in [Table 6-2](#). The dose reduction indicated as “recommendations” are provided to assist investigators in the event the patient experiences toxicity. However, deviations from “mandatory” dose interruptions and/or reductions are not allowed and mandatory interruptions or reductions must be strictly followed. Re-escalation to asciminib 40 mg BID is permitted if a change in the patient’s individual benefit/risk assessment at the lower dose level is seen. Re-escalation will be allowed only once for any given patient on the asciminib arm per protocol. Permanent treatment discontinuation is mandatory for specific events indicated as such in [Table 6-2](#). Any dose changes must be recorded on the Dosage Administration Record eCRF.

[figure not shown]
A patient must discontinue treatment with either asciminib or bosutinib if, after treatment is resumed at a lower dose level, the toxicity recurs with the same or worse severity, except for recurrence of cytopenias ([Table 6-2](#)). If a patient requires a dose interruption of > 28 days for each non-hematologic toxicity, then the patient must be discontinued from the study treatment. If a hematologic toxicity (cytopenia Grade 3 or 4) lasts for more than 42 days without recovery to at least a Grade 2, despite TKI interruption and adequate management (including hematopoietic growth factors), then the patient must be discontinued from the study treatment.

Table 6-2 Criteria for dose reduction/interruption and re-initiation of asciminib and bosutinib treatment for adverse drug reactions

[figure not shown]
Dose modifications for both asciminib and bosutinib		
Please note that if a patient requires a dose interruption of > 28 days for each toxicity, then the patient must be discontinued from the study treatment		
Worst toxicity CTCAE Grade 4.03	Asciminib	Bosutinib
Investigations (Hematologic) If a hematologic toxicity (cytopenia Grade 3 or 4) lasts for more than 42 days without recovery to at least a Grade 2, despite TKI interruption and adequate management (including hematopoietic growth factors), then the patient must be discontinued from the study treatment.		
Neutropenia (ANC)		

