Isolated total Bilirubin elevation		
> ULN – 1.5 x ULN	Recommendation: Maintain dose level	Recommendation: Maintain dose level
> 1.5 - 3.0 x ULN	Recommendation: Hold dose. Monitor LFTs ^b weekly, or more frequently if clinically indicated, until resolved to ≤ 1.5 x ULN: if resolved in ≤ 14 days, then maintain dose level if resolved in > 14 days, then reduce dose ↓ 1 dose level	Recommendation: Hold dose. Monitor LFTs ^b weekly, or more frequently if clinically indicated, until resolved to ≤ 1.5 x ULN: if resolved in ≤ 14 days, then maintain dose level if resolved in > 14 days, then reduce dose ↓ 1 dose level
> 3.0 - 10.0 x ULN*	Mandatory: Hold dose. Monitor LFTs ^b weekly, or more frequently if clinically indicated, until resolved to ≤ 1.5 x ULN: if resolved in ≤ 14 days, then reduce dose ↓ 1 dose level if resolved in > 14 days, then discontinue patient from study drug treatment. The patient should be monitored weekly (including LFTs ^b), or more frequently if clinically indicated, until total bilirubin have resolved to baseline or stabilization over 4 weeks.	Mandatory: Hold dose. Monitor LFTs ^b weekly, or more frequently if clinically indicated, until resolved to ≤ 1.5 x ULN: if resolved in ≤ 14 days, then reduce dose ↓ 1 dose level if resolved in > 14 days, then discontinue patient from study drug treatment. The patient should be monitored weekly (including LFTs ^b), or more frequently if clinically indicated, until total bilirubin have resolved to baseline or stabilization over 4 weeks.
> 10.0 x ULN*	Mandatory: Permanently discontinue patient from study drug treatment. The patient should be monitored weekly (including LFTs ^b), or more frequently if clinically indicated, until total bilirubin have resolved to baseline or stabilization over 4 weeks.	Mandatory: Permanently discontinue patient from study drug treatment. The patient should be monitored weekly (including LFTs ^b), or more frequently if clinically indicated, until total bilirubin have resolved to baseline or stabilization over 4 weeks.
Isolated AST or ALT elevation		
> ULN - 3.0 x ULN	Recommendation: Maintain dose level	Recommendation: Maintain dose level

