Dose modifications for both asciminib and bosutinib		
Please note that if a patient requires a dose interruption of > 28 days for each toxicity, then the patient must be discontinued from the study treatment		
Worst toxicity CTCAE Grade 4.03	Asciminib	Bosutinib

If combined elevations of AST or ALT and total bilirubin do not meet the defined thresholds, please follow the instructions for isolated elevation of total bilirubin and isolated elevation of AST/ALT, and take a conservative action based on the degree of the elevations (e.g. discontinue treatment at the situation when hold dose is needed for one parameter and discontinue treatment is required for another parameter). After all elevations resolve to the defined thresholds that allow treatment re-initiation, re-start the treatment either at the same dose or at one dose lower if meeting a criterion for dose reduction
 
^d “Cholestasis” defined as ALP elevation (>2.0 x ULN and R value <2) in patients without bone metastasis, or elevation of ALP liver fraction in patients with bone metastasis
 
Note: The R value is calculated by dividing the ALT by the ALP, using multiples of the ULN for both values. It denotes whether the relative pattern of ALT and/or ALP elevation is due to cholestatic (R ≤ 2), hepatocellular (R ≥ 5), or mixed (R >2 and < 5) liver injury
 
* Note: If total bilirubin > 3.0 x ULN is due to the indirect (non-conjugated) component only, and hemolysis as the etiology has been ruled out as per institutional guidelines (e.g., review of peripheral blood smear and haptoglobin determination), then ↓ 1 dose level and continue treatment at the discretion of the investigator.
 
** Note: A CT scan or other imaging study to assess the pancreas, liver, and gallbladder must be performed within 1 week of the first occurrence of any ≥ Grade 3 of amylase and/or lipase. If asymptomatic Grade 2 elevations of lipase and/or amylase occur again at the reduced dose, patients will be discontinued permanently from study treatment.
 
*** Note: antidiarrheal medication is recommended at the first sign of abdominal cramping, loose stools or overt diarrhea
		

[figure not shown]

Table 6-3 Dose reduction steps for asciminib and bosutinib

Dose reduction*			
	Starting dose level – 0	Dose level – 1	
Asciminib BID	40 mg tablet BID (total daily dose 80 mg)	20 mg tablet BID (total daily dose 40 mg)	
*Dose reduction should be based on the worst toxicity demonstrated at the last dose.			

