Asciminib dose reduction below total daily 40 mg is not allowed. 20 mg tablets will be dispensed to patients in the instance of dose reduction.			
Dose reduction*			
	Starting dose level – 0	Dose level – 1	Dose level – 2
Bosutinib QD	500 mg (1-500 mg tablet QD)	400 mg (4-100 mg tablets QD)	300 mg (3-100 mg tablets QD)
* Dose reduction should be based on the worst toxicity demonstrated at the last dose.			
Bosutinib dose reduction below total daily 300 mg is not allowed. 100 mg tablets will be dispensed to patients in the instance of dose reduction.			

[figure not shown]

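### Criterion 7 admits Gilbert's patients with raised total bilirubin, but the isolated-bilirubin rows of Table 6-2 make no allowance for an unchanged baseline value

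*Combined protocol and SAP*

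**What the plan says.** **Entry.** Criterion 7 in Section 5.2 (Amendment 3) limits total bilirubin to 1.5 x ULN, except for patients with Gilbert's syndrome, "who may only be included if total bilirubin" is no more than 3.0 x ULN or direct bilirubin is no more than 1.5 x ULN. The two limbs are joined by 'or', so a low direct fraction alone qualifies a patient whose total exceeds 3.0 x ULN.

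**On treatment.** Table 6-2 in Section 6.3.1 has the same isolated-bilirubin rows for both arms:

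- >1.5-3.0 x ULN: "Recommendation: Hold dose. Monitor LFTs" weekly until the value is at or below 1.5 x ULN. The dose is kept if that takes up to 14 days and reduced one level if it takes longer.
- >3.0-10.0 x ULN: a mandatory hold with the same 1.5 x ULN target. The dose is reduced if the value resolves within 14 days; "if resolved in > 14 days, then discontinue patient from study drug treatment".
- Footnote *, marked only on the rows above 3.0 x ULN, applies if the elevation "is due to the indirect (non-conjugated) component only" and hemolysis has been ruled out. The instruction is then to go down one "dose level and continue treatment at the discretion of the investigator".

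**Force of the rows.** Section 6.3.1 says that reductions labelled as recommendations "are provided to assist investigators in the event the patient experiences toxicity". Departures from mandatory ones are not allowed. The table header requires discontinuation "if a patient requires a dose interruption of > 28 days for each toxicity".

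**The concern.** The protocol deliberately lets in patients whose resting total bilirubin is above 1.5 x ULN, then uses 1.5 x ULN as the level to which bilirubin must fall before drug is restarted. A patient whose bilirubin has not moved since screening can therefore meet a hold or a dose reduction under the text as written.

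These patients have already had at least two TKIs, and Section 2.2 describes the options left after bosutinib failure as limited. Losing the assigned drug, or half of the asciminib dose, for a benign value accepted at entry would be a poor outcome for the patient. In an open-label trial, sites may also resolve the ambiguity differently from one another.

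**Working it through.** No figure in the plan bears on this, so the check sets the thresholds side by side. The values 2.0 and 3.5 x ULN are illustrations, not figures from the documents.

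| Stable total bilirubin (Gilbert's) | Eligible under criterion 7? | Table 6-2 row | Literal consequence |
|---|---|---|---|
| 2.0 x ULN | Yes, total limb | >1.5-3.0, recommendation | Advised hold to 1.5 x ULN, which is never reached; no footnote relief; discontinuation after 28 days if the hold is kept |
| 3.5 x ULN, direct at most 1.5 x ULN, footnote * conditions not met | Yes, direct limb | >3.0-10.0, mandatory | Hold, then discontinuation after 14 days |
| 3.5 x ULN, direct at most 1.5 x ULN, indirect only, hemolysis excluded | Yes, direct limb | >3.0-10.0 with footnote * | Treatment continues one dose level lower, although nothing has changed |

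**Timing of the first case.** Table 7-1 schedules chemistry at Week 2 Day 1, which is Day 8. A hold begun then reaches 28 days on Day 8 + 28 = Day 36. Taking Week 24 as Days 162 to 168, that is (162 - 36)/7 = 18.0 to (168 - 36)/7 = 18.9 weeks before the primary assessment.

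**Size of the dose step (Table 6-3).** Asciminib goes from 80 to 40 mg a day: 1 - 40/80 = 50%. "Asciminib dose reduction below total daily 40 mg is not allowed", so this is also the last step. Section 6.3.1 permits one return to 40 mg BID if the patient's benefit/risk assessment changes. Bosutinib goes from 500 to 400 mg: 1 - 400/500 = 20%, with 300 mg still available.

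**Is baseline used elsewhere?** Yes:

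- Creatinine Grade 2 can restart at Grade 1 or baseline.
- Grade 3 amylase/lipase has the same alternative target.
- The combined AST/ALT-bilirubin row has a separate criterion for patients with elevated baseline values.
- The DILI rule in Section 6.3.3.1 also treats an elevated baseline separately.

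In the isolated-bilirubin rows, baseline appears only as an end point for follow-up monitoring above 3.0 x ULN. It is never a hold or restart threshold. The parameter with an explicit entry exception is thus one that lacks a baseline clause where it acts.

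**The case against.** The best answer is scope. Table 6-2 is titled as covering adverse drug reactions, and Section 6.3.1 introduces it for patients who do not tolerate the schedule. The adverse-event definition in Section 8.1.1 (Amendment 1 text) requires something to appear or worsen. A Gilbert's value known before the first dose is none of these. Chemistry is also drawn at Week 1 Day 1, so a fully literal reading could advise holding a drug not yet started. This probably is what the sponsor intends. But the rows are written as absolute multiples of ULN, no sentence exempts an unchanged value, and other rows show that the protocol states a baseline allowance when it wants one.

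A reader might infer that the protocol forces Gilbert's patients off treatment. It does not do so generally. The >1.5-3.0 x ULN row is advisory, and it does state a restart target; the target is just out of reach for a stable raised value. An investigator may decline the hold, and the 28-day rule applies only when an interruption is required. Above 3.0 x ULN, footnote * already keeps the indirect-only pattern on drug, and the asciminib reduction can be reversed once at the investigator's discretion.

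Caution is also defensible on safety grounds. Section 1.2.1.1 lists the liver among the potential target tissues, and Section 1.2.1.2 reports 35 patients treated at 40 mg BID. That supports keeping the liver safety rules. It does not explain why an unchanged accepted value should lead to a hold or dose reduction.

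**Conclusion.** The mismatch between criterion 7 and the isolated-bilirubin rows is real and stands in the Amendment 3 text. It goes beyond missing detail because the row above 3.0 x ULN is mandatory, so following it exactly gives the wrong action for a stable eligible patient. Severity is minor. Few patients are likely to be affected, and the documents do not say how many have Gilbert's syndrome. The conclusion assumes that the rows are applied literally to a value unchanged since entry.

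Two stronger inferences are not supported:

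- **Bias or loss of power.** The rows are the same in both arms, a hold is not itself non-response, and there is no patient count from which to derive an effect. The Amendment 1 text of Section 10.4.3 counts discontinuation before Week 24 as non-response, but the Amendment 3 text of that section is not in the supplied document.
- **A known efficacy cost of the asciminib dose cut.** The simulation in Section 1.2.1.2 gives about 33% (24-42%) at 20 mg BID against 41% (31-51%) at 40 mg BID at 6 months. The intervals overlap, the outcome is a 1-log reduction rather than MMR, and re-escalation is possible.

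**What to change.** At the next amendment:

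1. In the >1.5-3.0 and >3.0-10.0 x ULN isolated-bilirubin rows, in both arms, change the recovery target to '<=1.5 x ULN or baseline (last value before first dose)'.
2. Add to footnote *: 'In known Gilbert's syndrome, an indirect-only elevation not clinically meaningfully above baseline, with hemolysis excluded, needs no hold or dose reduction.' Mark the footnote on the >1.5-3.0 x ULN row as well, since it now appears only on the higher rows. A strict at-or-below-baseline wording would bring the rule back at the first reading slightly above baseline.
3. Leave the combined AST/ALT-bilirubin row and the DILI rule unchanged as the safety net.

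The cost is one phrase in two rows and one sentence. No new scheduled assessment is needed: footnote b already fractionates bilirubin above 2.0 x ULN, and the central chemistry panel (Table 7-4, Amendment 1 text) lists direct and indirect bilirubin. The downside is that a few patients stay at full dose with a stable raised indirect bilirubin although the liver is a potential target tissue. They would do so under monitoring already planned.

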5.3 Exclusion criteria

Patients eligible for this study must not meet **any** of the following criteria:

1. Known presence of the T315I or V299L mutation at any time prior to study entry
2. Known second chronic phase of CML after previous progression to AP/BC
3. Previous treatment with a hematopoietic stem-cell transplantation
4. Patient planning to undergo allogeneic hematopoietic stem cell transplantation
5. Cardiac or cardiac repolarization abnormality, including any of the following:
 - History within 6 months prior to starting study treatment of myocardial infarction (MI), angina pectoris, coronary artery bypass graft (CABG)
 - Clinically significant cardiac arrhythmias (e.g., ventricular tachycardia), complete left bundle branch block, high-grade AV block (e.g., bifascicular block, Mobitz type II and third degree AV block)
 - QTcF at screening $\geq 450 \text{ msec}$ (male patients), $\geq 460 \text{ msec}$ (female patients)
 - Long QT syndrome, family history of idiopathic sudden death or congenital long QT syndrome, or any of the following:

- Risk factors for Torsades de Pointes (TdP) including uncorrected hypokalemia or hypomagnesemia, history of cardiac failure, or history of clinically significant/symptomatic bradycardia
 - Concomitant medication(s) with a “Known risk of Torsades de Pointes” per www.crediblemeds.org/ that cannot be discontinued or replaced 7 days prior to starting study drug by safe alternative medication.
 - Inability to determine the QTcF interval
6. Severe and/or uncontrolled concurrent medical disease that in the opinion of the investigator could cause unacceptable safety risks or compromise compliance with the protocol (e.g. uncontrolled diabetes, active or uncontrolled infection, pulmonary hypertension)
 7. History of acute pancreatitis within 1 year of study entry or past medical history of chronic pancreatitis
 9. History of acute or chronic liver disease
 10. Known presence of significant congenital or acquired bleeding disorder unrelated to cancer
 11. History of other active malignancy within 3 years prior to study entry with the exception of previous or concomitant basal cell skin cancer and previous carcinoma in situ treated curatively
 12. Known history of Human Immunodeficiency Virus (HIV), chronic Hepatitis B (HBV), or chronic Hepatitis C (HCV) infection. Testing for Hepatitis B surface antigen (HBs Ag) and Hepatitis B core antibody (HBcAb / anti HBc) will be performed at screening
 13. Impairment of gastrointestinal (GI) function or GI disease that may significantly alter the absorption of study drug (e.g. ulcerative disease, uncontrolled nausea, vomiting, diarrhea, malabsorption syndrome, small bowel resection, or gastric bypass surgery)
 - 14a. Treatment with medications that meet one of the following criteria and that cannot be discontinued at least one week prior to the start of treatment with study treatment
 - Moderate or strong inducers of CYP3A
 - Moderate or strong inhibitors of CYP3A
 15. Previous treatment with or known/ suspected hypersensitivity to asciminib or any of its excipients.
 16. Previous treatment with or known/ suspected hypersensitivity to bosutinib or any of its excipients.
 17. Participation in a prior investigational study within 30 days prior to randomization or within 5 half-lives of the investigational product, whichever is longer
 18. Pregnant or nursing (lactating) women
 - 19a. Women of child-bearing potential, defined as all women physiologically capable of becoming pregnant, unless they are using highly effective methods of contraception during dosing and for 3 days after last dose of asciminib and one month after last dose of bosutinib. Highly effective contraception methods include:

- Total abstinence (when this is in line with the preferred and usual lifestyle of the subject. Periodic abstinence (e.g., calendar, ovulation, symptothermal, post-ovulation methods) and withdrawal are not acceptable methods of contraception)
- Female sterilization (have had surgical bilateral oophorectomy (with or without hysterectomy) total hysterectomy or bilateral tubal ligation at least six weeks before taking study treatment). In case of oophorectomy alone, only when the reproductive status of the woman has been confirmed by follow up hormone level assessment
- Male sterilization (at least 6 months prior to screening). The vasectomized male partner should be the sole partner for that subject.
- Use of oral, injected or implanted hormonal methods of contraception or placement of an intrauterine device (IUD) or intrauterine system (IUS) or other forms of hormonal contraception that have comparable efficacy (failure rate <1%), for example hormone vaginal ring or transdermal hormone contraception.
- In case of use of oral contraception women should have been stable on the same pill for a minimum of 3 months before taking study treatment.
- Women are considered post-menopausal and not of child bearing potential if they have had 12 months of natural (spontaneous) amenorrhea with an appropriate clinical profile (e.g. age appropriate, history of vasomotor symptoms) or have had surgical bilateral oophorectomy (with or without hysterectomy), total hysterectomy or bilateral tubal ligation at least six weeks before taking study medication. In the case of oophorectomy alone, women are considered post-menopausal and not of child bearing potential only when the reproductive status of the woman has been confirmed by follow up hormone level assessment.

6 Treatment

[figure not shown]
